16.2 POST-OP RADIOGRAPHIC IMAGES

The categorical variables to be described are, N and (%):

- Post-op radiographic image: Medio-Lateral projection (ML)
- Post-op radiographic image: Antero-Posterior projection (AP)
- Number of additional radiographic images to upload (1 / 2)

17 DISCHARGE VISIT

This analysis will be performed on FAIS population.

The descriptive statistic (Mean, SD, Median, Q₁, Q₃, Min, Max) will be shown for the following continuous variable:

- Time from surgery to Discharge (days) (calculated as Date of discharge minus date of surgery)

The categorical variable to be described is, N and (%):

- Time from surgery to Discharge (days) within the time windows estimated in the protocol (5-9 days)? (Yes / No)

18 PLASTER OR IMMOBILIZER REMOVAL VISIT

This analysis will be performed on FAIS population.

18.1 VISIT INFORMATION

The descriptive statistic (Mean, SD, Median, Q₁, Q₃, Min, Max) will be shown for the following continuous variable:

- Time from surgery to date of removal (months) (calculated as Date of removal minus date of surgery)

The categorical variable to be described is, N and (%):

- Time from surgery to removal visit (months) within the time windows estimated in the protocol (1.5-2.5 months)? (Yes / No)

18.2 CLINICAL EXAMINATION

The categorical variables to be described are, N and (%):

- Has the bone reached a satisfactory consolidation? (Yes / No / Partially)
- The patient can stand up? (Yes / No (Non-weight-bearing)), if 'Yes':
 - Weight-bearing Protocol (if not prescribed by surgeon, report what is known) (Toe-touch weight-bearing (TTWB) / Partial weight-bearing (PWB)/ Full weight-bearing (FWB))
 - The patient walks? (Yes / No)
- How frequent did the patient reported pain at the affected limb before JTIN application? (Never / Some of the days / About half of the days / Most of the days /Everyday), is not equal to 'Never' VAS Pain Score according to the patient will be described (Mean, SD, Median, Q₁, Q₃, Min, Max)
- Was the pain pharmacologically treated? (Yes / No / unknown)

18.3 RADIOGRAPHIC IMAGES

The categorical variables to be described are, N and (%):

- Radiographic image: Medio-Lateral projection (ML)
- Radiographic image: Antero-Posterior projection (AP)
- Number of additional radiographic images to upload (1 / 2)

19 BONE CONSOLIDATION VISIT

This analysis will be performed on FAIS population.

19.1 VISIT INFORMATION

The descriptive statistic (Mean, SD, Median, Q₁, Q₃, Min, Max) will be shown for the following continuous variable:

- Time from surgery to Bone Consolidation visit (months) (calculated as Date of bone consolidation minus date of surgery)

The categorical variable to be described is, N and (%):

- Time from surgery to Bone Consolidation visit (months) within the time windows estimated in the protocol (3-7 months)? (Yes / No)

19.2 CLINICAL EXAMINATION

The categorical variables to be described are, N and (%):

- Has the bone reached a satisfactory consolidation? (Yes / No / Partially), is not equal to 'Yes' answer this question:
 - Bone consolidation is expected at this visit, please explain why the patient didn't reach bone consolidation
- The patient can stand up? (Yes / No (Non-weight-bearing)), if 'Yes':
 - Weight-bearing Protocol (if not prescribed by surgeon, report what is known) (Toe-touch weight-bearing (TTWB) / Partial weight-bearing (PWB)/ Full weight-bearing (FWB))
 - The patient walks? (Yes / No)
- Calculation double, If 'Calculation double' is equal to '1' answer this question
 - Explain why the patient cannot stand if bone is consolidated
- How frequent did the patient reported pain at the affected limb before JTIN application? (Never / Some of the days / About half of the days / Most of the days /Everyday), is not equal to 'Never' VAS Pain Score according to the patient will be described (Mean, SD, Median, Q₁, Q₃, Min, Max)
- Was the pain pharmacologically treated? (Yes / No / unknown)

19.3 ROM (RANGE OF MOTION)

The categorical variables to be described are, N and (%):

- Which Range of Motion are available for this patient?
 - None

- Knee Flexion
- Knee Extension
- Hip Flexion
- Hip Extension
- Hip Abduction
- Hip Internal Rotation (supine)
- Hip External Rotation (supine)
- Ankle Joint Dorsiflexion
- Ankle Joint Plantarflexion

The descriptive statistic (Mean, SD, Median, Q₁, Q₃, Min, Max) will be shown for the following continuous variables:

- ROM Knee Flexion
- ROM Knee Extension
- ROM Hip Flexion
- ROM Hip Extension
- ROM Hip Abduction
- ROM Hip Internal Rotation (supine)
- ROM Hip External Rotation (supine)
- ROM Ankle Joint Dorsiflexion
- ROM Ankle Joint Plantarflexion

19.4 RADIOGRAPHIC IMAGES

The categorical variables to be described are, N and (%):

- Radiographic image: Medio-Lateral projection (ML)
- Radiographic image: Antero-Posterior projection (AP)
- Number of additional radiographic images to upload (1 / 2)

20 2ND FOLLOW-UP VISIT

This analysis will be performed on FAIS population.

20.1 VISIT INFORMATION

The descriptive statistic (Mean, SD, Median, Q₁, Q₃, Min, Max) will be shown for the following continuous variable:

- Time from surgery to 2nd follow up visit (months) (calculated as 2nd follow visit Date minus date of surgery)

The categorical variable to be described is, N and (%):

- Time from surgery to 2nd follow up visit (months) within the time windows estimated in the protocol (8-10 months)? (Yes / No)

20.2 CLINICAL EXAMINATION

The categorical variables to be described are, N and (%):

- Has the bone maintained a satisfactory consolidation? (Yes / No / Partially), is not equal to 'Yes' answer this question:
 - Bone consolidation is expected at this visit, please explain why the patient didn't reach bone consolidation and if there is any change between previous visit:
- The patient can stand up? (Yes / No (Non-weight-bearing)), if 'Yes':
 - Weight-bearing Protocol (if not prescribed by surgeon, report what is known) (Toe-touch weight-bearing (TTWB) / Partial weight-bearing (PWB)/ Full weight-bearing (FWB)
 - The patient walks? (Yes / No)
- Calculation double, If 'Calculation double' is equal to '1' answer this question
 - Explain why the patient cannot stand if bone is consolidated
- How frequent did the patient reported pain at the affected limb before JTIN application? (Never / Some of the days / About half of the days / Most of the days /Everyday), is not equal to 'Never' VAS Pain Score according to the patient will be described (Mean, SD, Median, Q₁, Q₃, Min, Max)
- Was the pain pharmacologically treated? (Yes / No / unknown)

20.3 ROM (RANGE OF MOTION)

The categorical variables to be described are, N and (%):

- Which Range of Motion are available for this patient?
 - None
 - Knee Flexion
 - Knee Extension
 - Hip Flexion
 - Hip Extension
 - Hip Abduction
 - Hip Internal Rotation (supine)
 - Hip External Rotation (supine)
 - Ankle Joint Dorsiflexion
 - Ankle Joint Plantarflexion

The descriptive statistic (Mean, SD, Median, Q₁, Q₃, Min, Max) will be shown for the following continuous variables:

- ROM Knee Flexion
- ROM Knee Extension
- ROM Hip Flexion
- ROM Hip Extension
- ROM Hip Abduction
- ROM Hip Internal Rotation (supine)
- ROM Hip External Rotation (supine)
- ROM Ankle Joint Dorsiflexion
- ROM Ankle Joint Plantarflexion

21 3ER FOLLOW-UP VISIT

This analysis will be performed on FAIS population.

21.1 VISIT INFORMATION

The descriptive statistic (Mean, SD, Median, Q₁, Q₃, Min, Max) will be shown for the following continuous variable:

- Time from surgery to 3er follow up visit (months) (calculated as 3er follow visit Date minus date of surgery)

The categorical variable to be described is, N and (%):

- Time from surgery to 3er follow up visit (months) within the time windows estimated in the protocol (23-25 months)? (Yes / No)

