PROCEDURES	One selected site, experienced in the treatment of pediatric patients with OI, where the usage of JTIN is already part of the normal clinical practice, will participate in this study. Investigator will screen patients treated (or planned to be treated) with JTIN to verify inclusion and exclusion criteria, to achieve the enrollment of 25 cases. With lost to follow-up percentage estimated at 20%, this will lead to a total of 20 evaluable cases, i.e. 20 implanted JTIN (some patients may contribute for more than one implant). Patients are prospectively and retrospectively enrolled in the study: they may have undergone JTIN implantation from the 1 st of January 2022. Enrolled patients, since this study is non-interventional and observational, will follow the standard medical practice of the site: no requirements regarding the treatment of patients will be imposed on the site or Principal Investigator and the Sponsor will not in any manner influence the treatment decisions. Data of enrolled subjects will be collected for this study up to 1 year from surgery. The hospital standard care usually, but not exclusively, includes: surgery, discharge and plaster removal visits, and then 3 other follow up visits up to 1 year from surgery (see "Visits and Assessments Schedule"). Visits frequency is estimated as average of the site normal clinical practice, actual visit timing for each patient will be performed according to investigators and hospital staff evaluation. The patient data will be systematically collected by the investigator in eCRF.
PLANNED INVESTIGATION PERIOD	Preparation: 4 months for ethics committee submission preparation and approval.

	
Enrolment period: 6 months from site initiation.
 
Live phase: Total of 1,5 year (18 months), i.e. 6 months of enrollment period plus 1 year of clinical data collection until the last patient completed follow-up.
 
Final phase: 6 months including final monitoring, database closure and Statistical and Clinical Study Report writing.
								

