7.3 Study duration

The study duration at the site is planned for 1,5 years (18 months), that includes the enrollment period of 6 months plus 1 year of data collection up to last patient last visit.

The study duration for each subject implant is approximately 1 year from the date of surgery, according to the visit schedule. Since the subjects will follow standard clinical care of the site

and due to the observational character of the study, the study duration for each subject can be slightly different according to the standard of care.

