10.2.7 Visit 6 - 3rd Follow-up Visit (1 year ± 1 month)

The investigator will collect information regarding changes in the concomitant medication, AEs and MDDs, if any. The investigator will also collect x-ray images of the treated limb, clinical examination, measure the Knee, Hip, Ankle ROM (as applicable) and also the weight-bearing protocol assigned to the patient. The bone consolidation will be assessed by surgeon experience and evaluating corticalization of at least three sides of the callus on the radiographs. The Gillette Functional Assessment questionnaire is collected and can performed by the investigator in presence or also by telephone or by mail with the parent (or legal representative) in a different day from the visit, according to hospital standard care.

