7 EXPLORATORY OBJECTIVE

The Gillette Functional Assessment Questionnaire will be collected, according to hospital standard care, before the surgery Visit 0 (screening)) and at 1 year follow up (Visit 6), to evaluate the changes after treatment.

[figure not shown]
The questionnaire is performed by the investigator the first time (i.e. before the surgery) observing the patient (in presence or eventually via telemedicine), and for the follow-up it can be performed by the investigator by telephone or by email with the parent (or legal representative). The Gillette Functional Assessment Questionnaire is not specific developed for OI patients but it is used in the hospital because no other score is currently available specifically for OI patients. The hospital is aware that other factors for OI patient can interfere with the score.

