10 STUDY DURATION

The study duration at the site is planned for 1,5 years (18 months), that includes the enrolment period of 6 months plus 1 year of data collection up to last patient last visit.

The study duration for each subject implant is approximately 1 year from the date of surgery, according to the visit schedule. Since the subjects will follow standard clinical care of the site and due to the observational character of the study, the study duration for each subject can be slightly different according to the standard of care.

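### SAP 21.1 sets the final-visit window at 23-25 months, but the protocol it cites gives 1 year ± 1 month (11-13 months)

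*SAP*

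**What the plan says.** For each of the five visits after surgery, the SAP summarises the time from surgery and then reports, as N (%), how many visits fell inside the protocol window. For the last visit, SAP 21.1 asks whether the time from surgery lies "within the time windows estimated in the protocol (23-25 months".

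The protocol heads the corresponding section (10.2.7) "Visit 6 - 3rd Follow-up Visit (1 year ± 1 month", and the schedule table in Protocol 4.1 gives the same window.

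The SAP elsewhere agrees with the protocol. SAP 7 has the Gillette questionnaire collected before surgery "and at 1 year follow up (Visit 6), to evaluate the changes after treatment". SAP 10 states: "The study duration for each subject implant is approximately 1 year from the date of surgery". On the length of data collection, the protocol synopsis says: "Data of enrolled subjects will be collected for this study up to 1 year from surgery".

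**The concern.** The SAP attributes to the protocol a window that the protocol does not contain. The interval is centred on 24 months, and neither document schedules a 2-year visit. Because the rule is explicit, a programmer following the SAP would code it as it stands.

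At stake is the reported timing of the visit that closes the 1-year observation period and supplies the follow-up Gillette score. The report would show few or no final visits on time, beside a continuous summary showing visits at about 12 months. A reader could take this for a failure of follow-up in a study meant to support keeping the CE mark.

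**Working it through.** **Inputs.** The nominal visit times and tolerances come from Protocol 4.1 and 10.2.3 to 10.2.7. The coded windows come from SAP 17, 18.1, 19.1, 20.1 and 21.1. The target of 20 evaluable nails and 25 enrolled comes from Protocol 12.3.

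**Step 1: reproduce the SAP windows.** Window = nominal time ± tolerance.

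| Visit | Protocol | Computed window | SAP window | Match |
|---|---|---|---|---|
| Discharge | 1 week ± 2 days | 7 ± 2 = 5-9 days | 5-9 days | yes |
| Plaster or immobilizer removal | 2 months ± 2 weeks | 1.54-2.46 months | 1.5-2.5 months | yes, rounded |
| Bone consolidation | 5 ± 2 months | 3-7 months | 3-7 months | yes |
| 2nd follow-up | 9 ± 1 months | 8-10 months | 8-10 months | yes |
| 3rd follow-up | 12 ± 1 months | 11-13 months | 23-25 months | **no** |

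The rule reproduces four of the five windows. For the 2nd follow-up, for example, the SAP has "within the time windows estimated in the protocol (8-10 months", which is exactly 9 ± 1. The fifth window equals 24 ± 1 instead of 12 ± 1.

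**Step 2: overlap.** The protocol window ends at 13 months and the SAP window starts at 23. The gap is 23 − 13 = 10 months, so no visit can satisfy both.

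**Step 3: could a visit at 23-25 months be in the data?** Protocol 7.3 says: "The study duration at the site is planned for 1,5 years (18 months". A nail implanted on the first day of prospective enrolment therefore has at most 18 months of follow-up within the planned study, which is 23 − 18 = 5 months short. Retrospective nails, implanted from 1 January 2022, could have hospital visits that late, but collection stops at 1 year from surgery. As planned, a visit at 23-25 months would not be collected.

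**Step 4: size of the error in the row.** Let n be the number of nails with a final visit and k the number of those seen at 11-13 months, with none at 23-25 months. The correct entry is k/n and the coded entry is 0/n.

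- n = 20, k = 20: 20/20 = 100% becomes 0/20 = 0%.
- n = 20, k = 10: 10/20 = 50% becomes 0%.
- Each on-schedule visit shifts the row by 1/20 = 5 points, or by 1/25 = 4 points if the denominator is 25.
- SAP 14 asks for a total and a valid percentage. With 25 nails, of which 20 have a final visit and all 20 are on schedule, the correct figures are 20/25 = 80% total and 20/20 = 100% valid. Both become 0%.

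Only visits at 11-13 or 23-25 months change class. A visit at 15 months, for example, is out of window under either rule.

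**Step 5: does anything else use the window?** Membership of the FAS and FAIS depends on the selection criteria (SAP 13). Adverse events (23.1), implant survival (24.1), bone union (24.2), fracture-free survival (24.3) and the Gillette comparison (25) do not filter on visit timing. Bone union is taken from the plaster removal and bone consolidation visits. The change in every endpoint result is 0.

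**The case against.** The mismatch itself cannot be defended. The best case on the other side is that it hardly matters: one figure in one descriptive row, with the correct distribution of visit times printed beside it, so that the slip gives itself away. Protocol 4.1 also describes the visit times as averages of site practice, so being out of window is not by itself a deviation. All of this stands. It limits the weight of the point but does not make the row correct.

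Four narrower objections also deserve an answer.

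- The 18-month argument covers only prospective nails. That is right. For retrospective nails the conclusion rests on the limit of 1 year from surgery.
- A mean near 12 months and 0% within 23-25 months are arithmetically compatible. That is also right. The row contradicts the protocol window it cites; the summary beside it would merely make the error visible.
- A swing from 100% to 0% assumes that every final visit is on schedule. It does, and the shift is smaller in proportion if fewer are.
- SAP 3 ties the SAP to protocol version 1.1, and the version of the protocol reviewed here could not be confirmed because its title page is not available. This does not rescue the figure, because SAP 7 and SAP 10 also put the final visit at 1 year.

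**Conclusion.** The point holds. The window in SAP 21.1 should be 11-13 months. As written, every final visit made on schedule is counted as out of window, which understates the on-time percentage by up to 100 points: 0/20 against 20/20 if all 20 evaluable nails are seen at 11-13 months. That upper figure assumes full attendance on schedule. The classification error itself needs no assumption, since the two windows do not overlap.

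The consequence is confined to this N (%) row. The primary, secondary and exploratory results and the analysis sets are unaffected. It should be corrected before the analysis is run, but it does not threaten the study's conclusions.

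**What to change.** In SAP 21.1, replace 23-25 months with 11-13 months, and make the same change in any SPSS syntax or table shell that already carries the figure. This aligns the SAP with the protocol window it cites and with its own sections 7 and 10. The cost is one figure: no endpoint, analysis set or table layout changes, and no protocol amendment is needed.

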21.2 CLINICAL EXAMINATION

The categorical variables to be described are, N and (%):

- Has the bone maintained a satisfactory consolidation? (Yes / No / Partially), is not equal to 'Yes' answer this question:
 - Bone consolidation is expected at this visit, please explain why the patient didn't reach bone consolidation and if there is any change between previous visit:
- The patient can stand up? (Yes / No (Non-weight-bearing)), if 'Yes':
 - Weight-bearing Protocol (if not prescribed by surgeon, report what is known) (Toe-touch weight-bearing (TTWB) / Partial weight-bearing (PWB)/ Full weight-bearing (FWB))
 - The patient walks? (Yes / No)
- Calculation double, If 'Calculation double' is equal to '1' answer this question
 - Explain why the patient cannot stand if bone is consolidated

- How frequent did the patient reported pain at the affected limb before JTIN application? (Never / Some of the days / About half of the days / Most of the days / Everyday), is not equal to 'Never' VAS Pain Score according to the patient will be described (Mean, SD, Median, Q₁, Q₃, Min, Max)
- Was the pain pharmacologically treated? (Yes / No / unknown)
- Was the Gillet Score performed at this visit? (Yes / No) is equal to 'Yes' Gillette Functional Assessment Questionnaire result will be described (Mean, SD, Median, Q₁, Q₃, Min, Max)

21.3 ROM (RANGE OF MOTION)

The categorical variables to be described are, N and (%):

- Which Range of Motion are available for this patient?
 - None
 - Knee Flexion
 - Knee Extension
 - Hip Flexion
 - Hip Extension
 - Hip Abduction
 - Hip Internal Rotation (supine)
 - Hip External Rotation (supine)
 - Ankle Joint Dorsiflexion
 - Ankle Joint Plantarflexion

The descriptive statistic (Mean, SD, Median, Q₁, Q₃, Min, Max) will be shown for the following continuous variables:

- ROM Knee Flexion
- ROM Knee Extension
- ROM Hip Flexion
- ROM Hip Extension
- ROM Hip Abduction
- ROM Hip Internal Rotation (supine)
- ROM Hip External Rotation (supine)
- ROM Ankle Joint Dorsiflexion
- ROM Ankle Joint Plantarflexion

21.4 RADIOGRAPHIC IMAGES

The categorical variables to be described are, N and (%):

- Radiographic image: Medio-Lateral projection (ML)

- Radiographic image: Antero-Posterior projection (AP)
- Number of additional radiographic images to upload (1 / 2)

22 STUDY EXIT VISIT

This analysis will be performed on FAIS population.

The categorical variables to be described are, N and (%):

- Reason for study exit
 - Subject completed protocol last visit
 - Nail removed
 - Subject does not meet inclusion criteria (a list will be shown)
 - Subject withdrew consent
 - Subject withdrawn by Investigator (a list will be shown)
 - Subject Death
 - Lost to follow-up
 - Subject had an AE that does not permit the continuation of the study (specify nr. of AE: a list will be shown)
 - Other Reason (a list will be shown)

23 PRIMARY OBJECTIVE

The primary objective of the study is to evaluate the clinical safety profile of JTIN within the scope of its intended purpose, when used according to the manufacturer IFU on a representative population of subjects and users.

To fulfil this objective, one safety endpoint will be evaluated:

- Percentage (%) of procedures with at least one serious/not serious adverse event certainly or possibly related to JTIN up to 1 year follow-up.**

This objective will be analysed through the descriptive analysis of the variables as detailed below:

This analysis will be performed on FAS/FAIS population.

23.1 ADVERSE EVENTS

The categorical variables to be described are, N and (%) and Clopper-Pearson confidence intervals will be shown at 95.0% as well, for the overall population and for subgroups of patients defined according to OI Type Diagnosis (Mild/Non-deforming / Severe / Highly Severe/Progressively deforming / Lethal) as defined in section 15.6 of this document:

- Patients with at least one adverse event
- Patients with at least one serious adverse event
- Patients with at least one related adverse event (considering related as Yes, certainly related and Yes, possibly)
- Patients with at least one serious related adverse event (considering related as Yes, certainly related and Yes, possibly)
- Procedures with at least one adverse event
- Procedures with at least one serious adverse event
- Procedures with at least one related adverse event (considering related as Yes, certainly related and Yes, possibly)
- Procedures with at least one serious related adverse event considering related as Yes, certainly related and Yes, possibly)

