4.1 Visits and Assessments Schedule

VISITS	PERIODS		ENROLLMENT		TREATMENT		FOLLOW-UP		
	Description	Number	Screening	Surgery	Hospital Discharge	Plaster or Immobilizer Removal	Bone consolidation assessment	2 nd Follow-up	3 rd Follow-up
Time Window	N/A			Day 0	1 week (± 2 days)	2 months (± 2 weeks)	5 months (± 2 months)	9 months (± 1 month)	1 year (± 1 month)
Information and non-opposition		X							
Inclusion / Exclusion Criteria		X							
Medical History		X							
Concomitant medication		X			X	X	X	X	X
Demographics		X							
X-ray/Fluoroscopy image		X				X	X	X	X
Clinical Examination		X				X	X	X	X
Gillette Functional Assessment Questionnaire		X							
Device application				X					
Range of motion		X				X	X	X	X
Weight bearing protocol		X				X	X	X	X
Safety Events			X		X	X	X	X	X
MDDs			X		X	X	X	X	X

Note: timelines and event frequency are estimated as average of the site normal clinical practice, actual visit/event timing for each patient will be performed according to investigators and hospital staff evaluation.

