24.1 IMPLANT SURVIVAL RATE

Implant survival rate: percentage of not exchanged nails up to 1 year follow-up.

The categorical variables to be described are, N and (%) and Clopper-Pearson confidence intervals will be shown at 95.0% as well, for the overall population and for subgroups of patients defined according to OI Type Diagnosis (Mild/Non-deforming / Severe / Highly Severe/Progressively deforming / Lethal) as defined in section 15.6 of this document:

- Number of procedures that Reason for study exit= Nail removed vs other reason

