24.3 POST TREATMENT FRACTURE-FREE SURVIVAL

The categorical variables to be described are, N and (%) and Clopper-Pearson confidence intervals will be shown at 95.0% as well, for the overall population and for subgroups of patients defined according to OI Type Diagnosis (Mild/Non-deforming / Severe / Highly Severe/Progressively deforming / Lethal) as defined in section 15.6 of this document:

- Number of patients with fracture(s) occurred (variable: "Bone fracture during or after treatment" in adverse event description + confirmation that the bone with fracture is the same where there is the implant*) in at least one procedure
- Number of procedures with fracture(s) occurred (variable: "Bone fracture during or after treatment" in adverse event description + confirmation that the bone with fracture is the same where there is the implant*)

* A list, with confirmation for each AE that the "fracture" is on the same bone or not, will be provided from Sponsor in order to confirm if the bone with fracture is the same where there is the implant.

The descriptive statistic (Mean, SD, Median, Q₁, Q₃, Min, Max) will be shown for the following continuous variable, for the overall population and for subgroups of patients defined according to OI Type Diagnosis (Mild/Non-deforming / Severe / Highly Severe/Progressively deforming / Lethal) as defined in section 15.6 of this document:

- Time to free fracture from surgery (months), per procedure, considered at the first Adverse Event onset date in which variable: "Bone fracture during or after treatment" in adverse event description has been checked. Calculated as the first adverse event onset date with a "Bone fracture during or after treatment" minus date of surgery.

Kaplan-Meier analyses will be provided for Time to free fracture. The median and the 95%CI as well as the number of events and patients censored will be provided.

The number of patients at risk will be displayed.

Event: if "Bone fracture during or after treatment" in adverse event description is clicked (which first occurs).

Time: Time to free fracture from surgery, as has been defined above.

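### SAP 23.1, 24.1 and 24.3 set no time limit from surgery for endpoints defined to 1-year follow-up, so events after 1 year could be counted in rates labelled 1-year

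*SAP*

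**What the plan says.** **Endpoint definitions.** SAP 23 defines the primary endpoint as "Percentage (%) of procedures with at least one serious/not serious adverse event certainly or possibly related to JTIN up to 1 year follow-up". SAP 24.1 is headed by "Implant survival rate: percentage of not exchanged nails up to 1 year follow-up", and SAP 24 gives fracture-free survival the same limit.

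**Counting rules.**
- SAP 23.1 counts "Procedures with at least one related adverse event (considering related as Yes, certainly related and Yes, possibly"), with no condition on onset date.
- SAP 24.1 counts "Number of procedures that Reason for study exit= Nail removed vs other reason". The removal date is not used.
- SAP 24.3 counts "Number of procedures with fracture(s) occurred", identified by an adverse-event category plus confirmation that the implanted bone is the one affected. It adds that "Kaplan-Meier analyses will be provided for Time to free fracture", and the listed outputs are the median, its confidence interval, and the numbers of events, censored and at risk. No 12-month estimate or truncation is given.

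**Length of follow-up.** The Procedures row of the protocol synopsis limits data collection to 1 year from surgery. The row on study duration per subject ties the limit to the 1-year visit. Protocol 7.2 follows each case to its last visit, or to implant removal if earlier. Protocol 4.1 and 10.2.7 put Visit 6 at 1 year ± 1 month, but the note in 4.1 says that "actual visit/event timing for each patient will be performed according to investigators and hospital staff evaluation", and Protocol 10.1 agrees. SAP 10 accepts that duration may differ slightly between subjects. SAP 21.1 gives the final-visit window as 23-25 months and attributes it to the protocol.

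**The concern.** A programmer who follows SAP 23.1, 24.1 and 24.3 literally would count every event recorded for a nail, whenever it occurred. Nails whose final visits fall at different times would contribute unequal time at risk to one percentage. Surgeries from 1 January 2022 are eligible, so some retrospective nails may already be past 1 year when their data are entered. SAP 21.1 would also flag a 24-month final visit as within window.

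At stake is whether the headline safety figure is the 1-year percentage that the objective names. With about 20 evaluable nails, one event moves it by 5 percentage points.

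**Working it through.** **1. The plan's own figures.** Protocol 12.3 assumes a 31% event rate and asks for an upper 95% limit of at most 60%. Clopper-Pearson is the SAP's interval method. With x = 0.31n events, the upper limit is 60.5% at n = 14 and 59.4% at n = 15, so the stated 15 procedures are reproduced. For the total, 20 / (1 − 0.20) = 25, as stated.

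**2. Effect of later final visits.** Inputs: a true 12-month rate of 31% (Protocol 12.3) and the final visit at t months for all nails. Assumed model: P(event by t) = 1 − exp(−H × (t/12)^k), with H = −ln(1 − 0.31) = 0.371. Setting k = 1 gives a constant hazard; k = 0.5 and k = 0.3 concentrate events early. The documents give no hazard shape, so k is an assumption.

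| All final visits at | k = 1 | k = 0.5 | k = 0.3 |
|---|---|---|---|
| 12 months | 31.0% | 31.0% | 31.0% |
| 13 months | 33.1% | 32.0% | 31.6% |
| 18 months | 42.7% | 36.5% | 34.2% |
| 24 months | 52.4% | 40.8% | 36.7% |

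Example: 18 months, k = 1: 1 − exp(−0.371 × 1.5) = 42.7%.

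At the upper edge of the protocol window the excess is 33.1 − 31.0 = 2.1 points under constant hazard, and less with early events. Among 20 nails that is 0.1 to 0.4 extra nails with an event. At 18 months it is 0.7 to 2.3 nails, and at 24 months 1.1 to 4.3.

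For fracture, the lowest literature figure in Protocol 11.1.6 (11.11%), taken as a 12-month rate under constant hazard, becomes 12.0% at 13 months, 16.2% at 18 and 21.0% at 24.

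**3. What single late events do.** Clopper-Pearson 95% intervals:
- 6/20 = 30%: 11.9% to 54.3%
- 7/20 = 35%: 15.4% to 59.2%
- 8/20 = 40%: 19.1% to 63.9%

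Two late events added to 6/20 take the upper limit past the 60% used for planning.

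**4. The opposite direction.** The implant analysis set in SAP 13 contains all JTIN applications in enrolled patients and has no minimum follow-up. A nail that leaves early without an event counts as event-free. As an extreme, if 5 of 25 nails (the planned 20%) left with no time observed and stayed in the denominator, 31% would read 0.31 × 20/25 = 24.8%.

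**The case against.** The best defence is that the limit is already in the plan. The Procedures row of the synopsis stops collection at 1 year from surgery, and Protocol 14.6 rules out collecting additional data. If both are followed, later events never reach the database. That stands in part: the documents support only that late events could enter. A reader might infer that they certainly will, but nothing shows how many final visits are late. The defence is incomplete because two other passages tie collection to the visit and the SAP applies no limit itself.

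A second defence is that 1-year follow-up can mean the 1-year visit, so that rule and label agree. This is a fair reading, but the SAP does not state it, and it still leaves risk time to vary with the visit date.

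Third, the study is descriptive and has no decision rule, and the interval for 6/20 dwarfs a 2-point shift. That is right when visits keep to the window. The 18- and 24-month rows are illustrations; Protocol 7.3 and SAP 10 expect about 1 year with slight differences.

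Fourth, parts are already handled. Kaplan-Meier accommodates unequal follow-up for fracture, and SAP 24.3 computes onset minus surgery date, so it would be wrong to say that no derivation uses dates. A case ends at its last visit, so removals after that are not counted. Adverse events are listed, so late ones could be traced. All this stands, but the simple proportions for all three endpoints remain without a limit.

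**Conclusion.** The point holds as a gap between how the endpoints are defined and how they are counted. Events after 1 year could enter rates labelled 1-year. For the primary endpoint the excess is at most about 2 percentage points on 31% if final visits keep to ± 1 month. If all final visits fell at 18 months, 31% would read about 34% to 43% over the hazard shapes tried. Both the late timing and the shapes are assumptions.

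Three stronger readings are not supported:
- **That the net bias is upward.** Early exits counted as event-free pull the other way, and neither number is known.
- **That the rate cannot be compared with any literature figure.** The documents do not give the follow-up lengths behind the literature range. One can say only that it is not reliably a 1-year figure.
- **That the 23-25 months in SAP 21.1 extends event counting to 2 years.** That window only classifies visits as inside or outside. It does conflict with the protocol, and nothing else in the SAP would exclude events up to such a visit.

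The correction should be made before database lock.

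**What to change.** 1. State in the SAP one analysis cut-off from each nail's surgery. The upper edge of the protocol's Visit 6 window (13 months) is preferable because it matches the planned visit; day 365 is the alternative. Choose one before the data are analysed.
2. In 23.1, 24.1 and 24.3, count only events with onset, or nail removal, on or before that day. List later events separately.
3. Censor the fracture Kaplan-Meier analysis at that day and report its 12-month estimate with the confidence interval.
4. Report how many nails left before 12 months without an event, since a cut-off alone does not correct for them.
5. Reconcile SAP 21.1 with Protocol 4.1 and 10.2.7. Reconcile the synopsis Procedures row with the row on study duration per subject and Protocol 7.2.
6. Confirm that the nail-removal date is captured; the documents do not list it explicitly.

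The cost is small. Event dates are recorded (Protocol 11.1.10) and surgery dates are already used (SAP 15.3 and 24.3), so this is one derivation rule and, provided the removal date is held, no new data. The downside is that a few late events may move from the headline rate to a separate line, which is why that line should be reported beside it.
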